### 4.4 General definitions

#### ***Study Treatment:***

Patients will be assigned to one of the two treatment (BAF312/Placebo) arms in a ratio of 1:1. Study treatment will be noted as BAF312/Placebo throughout this document and CSR deliverables.

Patients and investigators (including all site staff) will remain blinded to study treatment throughout the study.

#### ***Study Day:***

The study day for safety/efficacy assessments (e.g. adverse event onset, laboratory abnormality occurrence, vital sign measurement, Electrocardiogram (ECG), PK sampling mRS scores, etc.,) will be calculated using the first administration of i.v. dose date as the reference date. For assessments occurring:

**on or after the first administration of i.v. dose date**, the study day will be calculated as (date of assessment/occurrence) – (date of first administration of i.v. dose) + 1. Then study day 1 will be the day of first administration of i.v. dose.

**before the first administration of i.v. dose date**, the study day will be calculated as (date of assessment/occurrence) – (date of first administration of i.v. dose).

For example, if a serious adverse event starts 1 day before the first administration of i.v. dose date, the study day displayed on the listing will be negative, i.e. -1.

***Baseline:***

For all evaluations, the last available assessment before or on the date/time of first dose is taken as 'baseline' value or 'baseline' assessment.

Commercially Confidential Information

***Unscheduled Assessment:***

In general, descriptive summary statistics will not include unscheduled/repeat assessment.

For all analyses regarding abnormal assessments or analyses based on worst post-baseline value (e.g. laboratory, ECGs, vital signs), all post-baseline values will be included (scheduled, unscheduled, repeat). All unscheduled and repeat measurements will be included in listings.

***Analysis visit window:***

No time-window will be applied in this study.

In summary by visit the scheduled EOS visit will be included. If appropriate EOS visit could be mapped to the next scheduled visit.

***On treatment:***

It corresponds to any event or any assessment occurring between the 1st study drug injection date and the last injection/intake date.

## **5 Statistical methods for primary objective**

### **5.1 Primary objective**

To obtain the first efficacy estimate of CCI BAF312 daily (7 days i.v. with titration followed by 7 days p.o.) compared to placebo on reducing absolute perihematoma edema (aPHE) volume on Day 14 after ICH.

#### **5.1.1 Variables**

The primary efficacy variable is the aPHE volume measured on Day 14, which will be measured from the CT images by a central reading lab.

The primary analysis will be done on the PPS. A sensitivity analysis will be done on the FAS.

#### **5.1.2 Descriptive analyses**

Summary statistics of aPHE will be presented by treatment at Day 14 in the same output as the inferential result.

#### **5.1.3 Statistical model, assumptions and hypotheses**

It is expected that the distribution of aPHE is right-skewed (as it is a positive-valued measurement), so a log-transformation will be applied. The log-transformed absolute PHE volume on Day 14 will be analyzed using analysis of covariance (ANCOVA) model, with

treatment as a classification factor and the baseline log-transformed aPHE as covariate. The mean difference (BAF312 vs. placebo) and its two-sided 90% CI will be calculated, and these estimates will be back-transformed to give adjusted geometric mean and the respective CV along with a geometric mean ratio and two-sided 90% CI of BAF312 vs. placebo. One-sided p-value will be provided to test superiority of BAF312 to placebo.

#### **5.1.3.1 Handling of Missing Data**

Every effort will be made to obtain complete data during clinical conduct of the study.

The analysis will be done on the available data recorded on the Day 14 CT scan.

Commercially Confidential Information

#### **5.1.3.2 Supportive Analyses**

Commercially Confidential Information

#### **5.1.3.3 Graphical presentation of results**

Commercially Confidential Information

Percentage of ordinal mRS score at Day 90 will be displayed by treatment.

### **5.2 Secondary objectives**

The secondary objectives are to assess the safety profile, and to evaluate the pharmacokinetics of BAF312 in ICH patients.

#### **5.2.1 Variables**

- Safety profile of BAF312 in ICH patients will be evaluated by continuous assessment of AEs/SAEs during the course of the study (90 days). Safety set will be used for this analysis.
- PK of BAF312 in ICH patients will be evaluated by PK measurements of plasma BAF312 concentrations at 0.5, 2 and 6 h after start of infusion during i.v. titration on Day 1; and before p.o. dosing on Days 8 and 14. PK Analysis set will be used.

## **5.2.2 Descriptive analyses**

Both secondary endpoints are descriptive in nature, there will not be any inferential statistics presented. Descriptive statistics will be presented for concentration vs time by treatment arm.

## **5.2.3 Statistical model, assumptions and hypotheses**

The analyses will be descriptive. No hypothesis will be tested.

### ***Safety profile of BAF312:***

The incidence of any treatment emergent adverse events (TEAEs), serious TEAEs overall and by severity will be summarized by treatment using frequency counts, percentages of patients and 95% Confidence Intervals (CIs) for percentages obtained using Clopper – Pearson method.

Treatment emergent adverse events are defined as any event starting or worsening on treatment (i.e. between the 1st study drug injection date and the last study drug injection/intake date).

These secondary safety endpoints will be summarized by treatment arm for the safety analysis set.

### ***PK of BAF312:***

Refer SAP section 6.

### **5.2.3.1 Model checking procedures**

There will be no imputation for missing values.

### **5.2.3.2 Graphical presentation of results**

Graphical presentation may be provided for most frequent TEAEs sorted by relative risk. For PK, refer section 6.

## **6 Statistical methods for Pharmacokinetic (PK) parameters**

One of the secondary objectives is to evaluate the pharmacokinetics of BAF312 in ICH patients.

### **6.1 Secondary Objective:**

PK of BAF312 in ICH patients will be evaluated by PK measurements of plasma BAF312 concentrations at 0.5, 2 and 6 h after start of infusion during i.v. titration on Day 1; and before p.o. dosing on Days 8 and 14. All PK analyses will be performed based on the PAS.

### **6.2 Variables**

As only sparse PK samples will be collected in the study, no PK parameters will be estimated. PK samples will be pooled with PK data of other available studies in order to assess the effect of various covariates on the plasma concentrations of BAF312 in patients with stroke due to ICH through a population pharmacokinetic analysis and it is not scope of this SAP.

Only evaluable PK concentration data will be used in the analyses and summary statistics.

Unscheduled samples will not be used for descriptive statistics. It will be flagged in the corresponding concentration listing.

Commercially Confidential Information

### **6.3 Descriptive analyses**

Commercially Confidential Information

Summary statistics will include mean (arithmetic and geometric), SD, CV (arithmetic and geometric), median, minimum and maximum. Concentrations below the limit of quantification will be treated as zero in summary statistics and excluded from geometric mean and geometric Coefficient of Variation (CV%) computation. Linear mean concentration vs. time will be graphically presented. In addition, individual patient concentration vs. time will also be presented.

BAF312 plasma concentration data will be listed by treatment, patient, and visit/sampling time point. All individual data will be listed on all randomized subjects and those excluded from the PK analysis will be flagged. Statistical model, assumptions and hypotheses

The analyses will be descriptive. No hypothesis will be tested.

## **7 Exploratory objectives**

### **7.1.1 Variables**

Commercially Confidential Information

## **7.1.2 Descriptive analyses**

Commercially Confidential Information

Commercially Confidential Information

## Commercially Confidential Information

## 8 Statistical methods for safety and tolerability data

The following safety analyses will be performed based on the Safety Set.

### 8.1 Variables

Adverse events, vital signs (blood pressure, pulse rate, body temperature), ECG intervals, laboratory measurements, as well as subject demographics, baseline characteristics, and treatment information.

### 8.2 Descriptive analyses

#### Subject demographics and other baseline characteristics

The FAS will be used for all patient demographic and baseline characteristic summaries and listings, unless otherwise specified.

All data for background and demographic variables will be listed by treatment and patient. Summary statistics will be provided by treatment. Descriptive statistics, frequency counts and percentages will be tabulated by treatment arm, as appropriate.

Baseline demographic includes following,

- Age (in years)
- Age category in years (<70; >=70)
- Sex (Male, Female)
- Race (Caucasian, Black, Asian, Native American, Pacific Islander, Unknown, Other)
- Ethnicity (Hispanic or Latino, East Asian, Southeast Asian, South Asian, West Asian, Russian, Mixed Ethnicity, Not Reported, Unknown, Other)
- Weight (kg)
- Height (cm)
- Body Mass Index (BMI) – calculated as  $\text{weight (kg)} / (\text{height (m)})^2$

Other baseline characteristics includes,

- Glasgow Coma Scale (GCS) total score
- GCS total score in categories (<13 a.u., >=13 a.u.)
- Baseline blood pressure includes systolic (mmHg), diastolic (mmHg), pulse (Beats/min), and Temperature (°C)

Commercially Confidential Information

### Commercially Confidential Information

- Baseline aPHE volume (mL)
- Baseline location of hematoma
- Time from first symptoms of ICH or last seen neurologically normal status (day). This time will be computed up to the start of study drug.

Patients who signed study informed consent and pharmacogenetic informed consent with date will be presented in listings by treatment and patient.

### ***Medical History***

Medical history and ongoing conditions will be listed by treatment arm. Medical history and current medical conditions will be coded using the Medical Dictionary for Regulatory Activities (MedDRA) terminology.

### **Patient disposition**

The FAS will be used for the patient disposition summaries. The summary by treatment arm will show:

- Number (%) of randomized patients who were not treated;
- Number (%) of randomized patients who were treated;
- Number (%) of patients who completed the study treatment;
- Number (%) of patients who discontinued the study treatment;
- Reasons for study treatment discontinuation.

Frequency counts and percentages of patients for each of analysis set will be presented separately by treatment. Any protocol deviation (selection criteria not met, patient not withdrawn as per protocol, key procedures not performed as per protocol, treatment deviation, prohibited concomitant medication, other Good Clinical Practice (GCP) deviation) will be tabulated by the deviation type and treatment.

All protocol deviations will be presented in a listing by treatment and patient. Summary of protocol deviation with categories will be presented by treatment.

### ***Data presented for screen failure patients***

- Screen failure patients will not be included any analysis.

### **Study drug exposure and compliance**

The total treatment lasts 14 days with two treatment phases (i.v. to p.o.) based on dose administration.

7 days of i.v. BAF312 with titration to the final daily dose Commercially Confidential Information

During the 7 days of i.v. infusion treatment, all patients must undergo a swallowing safety evaluation per the treating hospital's institutional guidelines and practices.

If the patients pass the swallowing safety evaluation, 7 days of CCI BAF312 p.o. QD.

Patients who do not successfully pass a swallowing safety evaluation must not be transitioned to the p.o. phase of treatment, and BAF312 must be discontinued after Day 7; but they should not be terminated from the study. These patients should continue to be followed as per the protocol assessment schedule.

Eligible patients who pass a swallowing safety evaluation will continue with 7-day p.o. phase of treatment with BAF312 CCI QD.

Information on the dose administration, amount, frequency (includes dose titration), reason for the dose change, start date and end date in eCRF pages collected for each of the treatment phase.

Overall study drug exposure, study drug exposure for individual phase (i.v. and p.o.) will be calculated as follows,

Overall drug exposure (days) =[date of last study treatment – date of first study treatment+1]

Study drug exposure in i.v. phase (days) =[date of last dose in i.v. phase– date of first dose in i.v. phase +1]

Study drug exposure in p.o. phase (days) =[date of last dose in p.o. phase– date of first dose in p.o. phase +1]

Overall drug exposure, study drug exposure in i.v. and p.o. phase will be summarized by treatment. In addition, frequency counts and percentages of patients who have dose decreases, increases in planned dose or dose interruptions, the corresponding reasons and average length of dose interruptions will be summarized separately for i.v. phase and p.o. phase.

Listing of drug administration will be presented with i.v. treatment phase on day 1-7 and another listing for p.o. phase on day 8-14.

During the 7 days of i.v. infusion treatment, all patients will undergo a swallowing safety evaluation. A listing will be provided for swallowing test by treatment.

***Compliance using pill count in p.o. phase:***

Study drug compliance of patients who transitioned from i.v. to p.o. phase will be evaluated using “Drug Accountability Oral Medication” eCRF page.

The relative consumed tablet count (%) is defined as the ratio of total count consumed to total count prescribed. Where the total count consumed is calculated as the sum of counts dispensed minus the sum of counts returned and where the prescribed count corresponds to the count prescribed by the investigator for a p.o. phase that the patient should have taken during this phase.

The relative consumed tablet will be summarized by treatment.

**Prior, concomitant and post therapies**

Prior and concomitant therapies are defined as any medication, and significant non-drug therapies administered to a subject preceding or coinciding with the study assessment period.

Concomitant medications entered into the database will be coded using the WHO Drug Reference List (WHO DRL), which employs the WHO Anatomical Therapeutic Chemical (WHO ATC) classification system.

Concomitant therapies will include medications and significant non-drug therapies taken during treatment phase. Prior therapies will include medications or significant non-drug therapies starting and ending prior to the start of study treatment.

Concomitant and prior therapies will be summarized by ATC class, preferred term and treatment arm using safety set. Medications starting prior to the start of study treatment and continuing after the start of study treatment will be counted in both summaries.

All prior and concomitant therapies will be listed.

### Vital signs

Vital signs will include pulse rate, systolic and diastolic blood pressure in supine position and temperature which will be assessed at the all visits from screening/baseline to 90 days.

Summary statistics of vital sign results and change from baseline will be provided by treatment and visit/time.

Change from baseline will only be summarized for patients with both baseline and post baseline values and will be calculated as:

$$\text{change from baseline} = \text{post baseline value} - \text{baseline value}.$$

**Table 8-1 Notable vital signs and body weight**

Vital Sign Variable	Notable Criteria
Pulse (beats/min)	>120 bpm or < 50 bpm
Systolic BP (mmHg)	≥ 160 mmHg or ≤ 90 mmHg
Diastolic BP (mmHg)	≥ 100 mmHg or ≤ 50 mmHg
Temperature (°C)	>38.3 °C/ 101°F
Body weight (kg)	More than 7% decrease from baseline weight

Listing will be provided with vital signs results and notable values will be flagged by treatment and patients. Box plot will be presented for each of vital sign parameter over visits by treatment.

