8.6.2 Vital signs

Vital signs will include pulse rate, systolic and diastolic blood pressure in supine position, respiratory rate, and temperature which will be assessed at the visits indicated in [Table 8-1](#).

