11.5.2 Safety

Vital signs

All vital signs data will be listed by treatment group, patient, and visit/time and if ranges are available abnormalities (and relevant orthostatic changes) will be flagged. Summary statistics will be provided by treatment and visit/time.

ECG evaluations

All ECG data will be listed by treatment group, patient and visit/time, abnormalities will be flagged. Summary statistics will be provided by treatment and visit/time.

Clinical laboratory evaluations

All laboratory data will be listed by treatment group, patient, and visit/time and if normal ranges are available abnormalities will be flagged. Summary statistics will be provided by treatment and visit/time.

Adverse events

All information obtained on adverse events will be displayed by treatment group and subject.

The number and percentage of patients with adverse events will be tabulated by body system and preferred term with a breakdown by treatment. A patient with multiple adverse events within a body system is only counted once towards the total of this body system.

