Table 17-1 Notable Vital Signs And Body Weight

Vital Sign Variable	Notable Criteria
Pulse (beats/min)	>120 bpm Or < 50 bpm
Systolic BP (mmHg)	≥ 160 mm Hg Or ≤ 90 mm Hg
Diastolic BP (mmHg)	≥ 100 mmHg Or ≤ 50 mmHg
Temperature (°C)	>38.3 °C/ 101°F
Body weight (kg)	± 7% from baseline weight

18 Appendix 4: Modified Rankin Scale

MODIFIED RANKIN SCALE (MRS)

Patient Name: _____

Rater Name: _____

Date: _____

Score	Description
0	No symptoms at all
1	No significant disability despite symptoms; able to carry out all usual duties and activities
2	Slight disability; unable to carry out all previous activities, but able to look after own affairs without assistance
3	Moderate disability; requiring some help, but able to walk without assistance
4	Moderately severe disability; unable to walk without assistance and unable to attend to own bodily needs without assistance
5	Severe disability; bedridden, incontinent and requiring constant nursing care and attention
6	Dead

TOTAL (0–6): _____

References

Rankin J. "Cerebral vascular accidents in patients over the age of 60."
Scott Med J 1957;2:200-15

Bonita R, Beaglehole R. "Modification of Rankin Scale: Recovery of motor function after stroke."
Stroke 1988 Dec;19(12):1497-1500

Van Swieten JC, Koudstaal PJ, Visser MC, Schouten HJ, van Gijn J. "Interobserver agreement for the assessment of handicap in stroke patients."
Stroke 1988;19(5):604-7

Commercially Confidential Information

Commercially Confidential Information

Commercially Confidential Information

Commercially Confidential Information

Commercially Confidential Information

Commercially Confidential Information

Commercially Confidential Information

Commercially Confidential Information

20 Appendix 6: Glasgow Coma Scale (GCS)

From: www.glasgowcomascale.org

GLASGOW COMA SCALE : Do it this way

GCS
at 40

EYES
VERBAL
MOTOR

Institute of Neurological Sciences NHS Greater Glasgow and Clyde

CHECK

For factors Interfering with communication, ability to respond and other injuries

OBSERVE

Eye opening, content of speech and movements of right and left sides

STIMULATE

Sound: spoken or shouted request
Physical: Pressure on finger tip, trapezius or supraorbital notch

RATE

Assign according to highest response observed

Eye opening

Criterion	Observed	Rating	Score
Open before stimulus	✓	Spontaneous	4
After spoken or shouted request	✓	To sound	3
After finger tip stimulus	✓	To pressure	2
No opening at any time, no interfering factor	✓	None	1

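### SAP vital-sign outputs depart from the protocol in two places: the weight flag covers loss only, and respiratory rate is left out

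*SAP*

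**What the plan says.** **Body weight.** Protocol Appendix 3, Table 17-1, sets the notable criterion for weight at ± "7% from baseline weight". SAP section 8.2, Table 8-1, sets it at "More than 7% decrease from baseline weight". Under that table the SAP says that, in the vital-signs listing, "notable values will be flagged by treatment and patients".

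**Respiratory rate.** Protocol section 8.6.2 defines the set: "Vital signs will include pulse rate, systolic and diastolic blood pressure in supine position, respiratory rate, and temperature". Protocol section 11.5.2 then requires: "All vital signs data will be listed by treatment group, patient, and visit/time and if ranges are available abnormalities" are to be flagged. It adds: "Summary statistics will be provided by treatment and visit/time".

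The SAP lists vital signs twice, without respiratory rate either time. Section 8.1 has "vital signs (blood pressure, pulse rate, body temperature"; section 8.2 has "Vital signs will include pulse rate, systolic and diastolic blood pressure in supine position and temperature". Section 8.2 attaches its listing, by-visit summary, change from baseline and box plot to that shorter set.

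**The concern.** The SAP says in section 4.2 that the data are analysed in line with section 11 of the protocol, as the SAP details it. A reader therefore expects the SAP to carry the protocol's rules over or to explain a departure. In these two places it does neither in the text that can be read.

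The weight row is the only row of the notable-value table that differs from the protocol. The SAP's sentence listing the vital signs otherwise follows the protocol's closely, with respiratory rate missing. Both differences look like slips rather than decisions.

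Assessing the safety profile is a secondary objective in a study of about 65 patients, and its safety analyses are descriptive. If the SAP is programmed as written, a protocol-notable weight gain passes through the listing unmarked. A measure that the protocol collects and promises to summarise by arm has no planned output.

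**Working it through.** The check is a comparison of text. No sample size, power or error rate enters, and the documents give no figure to reproduce.

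**Step 1. Notable criteria, row by row** (protocol Table 17-1 against SAP Table 8-1):

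| Variable | Protocol | SAP |
|---|---|---|
| Pulse | >120 or <50 bpm | same |
| Systolic BP | ≥160 or ≤90 mmHg | same |
| Diastolic BP | ≥100 or ≤50 mmHg | same |
| Temperature | >38.3 °C | same |
| Body weight | ± 7% from baseline | decrease of more than 7% only |
| Respiratory rate | no row | no row |

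Four of the five rows agree; weight does not.

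**Step 2. What the weight difference does.** Take an assumed baseline of 80 kg, for illustration only.

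- Protocol limits: 80 × 0.93 = 74.4 kg and 80 × 1.07 = 85.6 kg.
- SAP rule: flag only below 74.4 kg.
- A rise to 86 kg is 86/80 − 1 = +7.5%. It lies outside the protocol limits and is not flagged under the SAP.
- At exactly 74.4 kg the SAP does not flag, because it requires more than 7%. The protocol does not say whether exactly 7% counts.

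**Step 3. Vital-sign lists:**

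| Variable | Protocol 8.6.2 | SAP 8.1 | SAP 8.2 |
|---|---|---|---|
| Pulse | yes | yes | yes |
| Blood pressure | yes | yes | yes |
| Temperature | yes | yes | yes |
| Respiratory rate | yes | no | no |
| Body weight | no | no | no |

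With blood pressure counted once, the protocol has four vital signs and the SAP covers three. With systolic and diastolic counted separately, it is five and four. Either way, one is missing.

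**Step 4. Which protocol instruction each omission departs from.**

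- Respiratory rate: the listing and the by-treatment, by-visit summary in protocol 11.5.2. It does not depart from a flagging rule, because 11.5.2 asks for flags only where ranges exist and Table 17-1 has none for respiratory rate.
- Weight: the criterion in Table 17-1 only. Weight is in neither document's vital-sign list, so the visible text asks for no by-visit weight summary that the SAP could have dropped.

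**The case against.** The strongest reply is that little depends on either mismatch.

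- The secondary safety endpoint is AEs and SAEs, not vital signs. Protocol section 9.1 makes clinically significant abnormal findings reportable as AEs, and SAP section 8.2 tabulates AEs by arm. **This stands**, and it limits the importance of the point.
- Notable vital signs are only marked in a listing. For ECG thresholds the SAP plans counts and proportions; for vital signs neither document does. **This stands.** A reader might infer that a by-arm comparison of weight gain has been lost, but none was planned in either document.
- The protocol mentions aspiration pneumonia, and a reader might infer that the SAP discards a respiratory safety signal that the protocol defines. **The documents do not support that.** Protocol section 3.7 says that the risk cannot be excluded, but that BAF312 is not believed to increase it. Table 17-1 defines no respiratory threshold, and respiratory infections would be reported as AEs.
- Most of the assessment schedule is absent from the text available, so post-baseline weighing cannot be confirmed. Outside the notable-value tables, the visible text mentions follow-up weight only in the renal-event work-up. **This stands as a caveat**, but the SAP's own decrease criterion already presupposes a post-baseline weight.
- The SAP refers back to protocol section 11, and output specifications are in separate documents (SAP section 1.1), so the omitted outputs might be produced anyway. **This stands in part.** It rules out saying that the data will never be reported, but the SAP wording still conflicts with the protocol.

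**Conclusion.** The point holds as two departures of the SAP from the protocol, both minor.

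1. Weight gains that are notable under protocol Table 17-1 would not be flagged in the SAP listing: one of the criterion's two directions is lost.
2. Respiratory rate has no planned listing, summary, change from baseline or box plot, although protocol 11.5.2 requires the listing and the summary.

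The effect is limited to descriptive safety outputs. The primary aPHE analysis, its power and the AE/SAE analysis do not change. How many patients would be affected cannot be derived from the documents.

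The conclusion assumes that the SAP is programmed as written and that no redacted or separate text explains or reverses the two differences. For weight, it also assumes that post-baseline values exist.

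**What to change.** **Weight.** Reconcile the weight row of SAP Table 8-1 with protocol Table 17-1 so that increases and decreases are both flagged, and state whether a change of exactly 7% counts. If the decrease-only rule is intended, give the reason in the SAP.

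**Respiratory rate.** Add it to the vital-sign lists in SAP sections 8.1 and 8.2, so that it gets the same listing, by-visit summary, change from baseline and box plot as the other vital signs. A flag is not needed for consistency with the protocol; if one is wanted, a notable range would have to be specified first, since neither document gives one.

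**Cost.** A few words in the SAP and minor programming. Respiratory rate is already a protocol assessment. Flagging weight gain uses the same post-baseline weights that the decrease criterion needs.
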